#### Special components of OPUS YOUNG

The OPUS YOUNG team has special focus on areas particularly critical for this group of adolescents:

 Special transition support will bridge the gap between child and adolescent psychiatry and adult psychiatry, or social care, by securing the patients a safe transfer from OPUS YOUNG treatment to continued standard treatment in child and adolescent or adult mental health services (depending on age at end of the two years OPUS YOUNG treatment). In contrast to standard care, patients in OPUS YOUNG will not be terminated from the intervention and transferred to adult psychiatry if they turn 18 years of age during the two years intervention period. The OPUS YOUNG team will follow the principles of the "NICE guidelines for supporting young people in their transition to adult services" [31]. Principles in the NICE guidance, emphasizes to allocate a named worker (in OPUS YOUNG; the case manager) to oversee, coordinate and delivery transition support and advocate for the young person if needed, and further, to ensure that the overall plan for supporting is revised if the young person is not in contact with services after transfer [31]. The transition to standard care will be scheduled approximately half a year in advance.

- 2) Individual school/employment support. In cooperation with the patients' school or educational/vocational institution, the case manager will support and encourage educational and vocational goals among all adolescents, including those who have dropped out of school or are at risk of doing so. To ensure that relevant education/vocation is provided, we will liaise with the patients' school and educational authority and with their parents. Mutual agreement determines whether a special educational needs' assessment is necessary. The case manager and the team will, in corporation with extern agents provide supported employment programs for those above compulsory school age who wish to find employment [102]. Case manager and the team will consider and motivate for other work-related activities or supported work when individuals are unable to attain a regular job or are unsuccessful in their attempts to find employment. To enable the patients' access to employment and educational opportunities, these efforts will be sensitive to the young person's needs and skill level and will be worked out in partnership with local stakeholders. OPUS YOUNG will follow the principles of the NICE guidelines for education, employment and occupational activities for children and young people with psychosis and schizophrenia [103].
- 3) Prevention and treatment of substance abuse are integrated in the OPUS YOUNG intervention and carried out by the case manager in collaboration with, and supervised by, consulting experts. A Cochrane review of psychosocial interventions for cannabis use disorder suggested that improvements in cannabis use, frequency and severity of dependence were most likely when the treatment offered were a combination of cognitive behavioral therapy (CBT) and motivational enhancement therapy (MET) [104]. This combination of CBT and MET as well as the use of gift cards and follow up sessions, have in a Danish randomized study shown to be very effectful in reducing and cessation of cannabis use among young people [105,106]. In

OPUS YOUNG we integrate this combination of CBT and MET as add on of 12 manualized sessions for those patients who have a misuse and who are motivated for treatment, with use the MOVE manual [107].

In general, and to ensure confidence and the opportunity to collaborate with the patient on minimization or cessation of misuse, the case manager will exercise a non-judgmental approach towards use of substances. OPUS YOUNG will follow the principles of NICE "Coexisting severe mental illness and substance misuse: assessment and management in healthcare settings" and consider the expected NICE guideline "Drug misuse prevention" [108]. We will also actively intervene to prevent initiation of smoking and promote smoking cessation, as this poses an additional severe threat to health [109]. From our prior studies including youth with psychosis, we know that tobacco use is high among these patients. In the TEA trial, 40% of 12-17 year old patients with early onset psychosis compared to 1% of healthy controls were smokers (p<0.001) [110].

#### Experts by experience

In OPUS YOUNG the use of "experts by experiences" also known as peer support, will be integrated as an independent and permanent part in psychoeducation for both patients, caregivers, and siblings. Furthermore, experts by experiences will contribute to the introduction of new team members and act as an expert panel like the OPUS panel. The OPUS panel was founded in 2009 by a group of young people who had been in treatment in EIS teams (OPUS) in Denmark and their relatives. The purpose of the panel is that the members with their personal history and through dissemination about living with an invisible disease helps to broaden the knowledge about the diagnosis of schizophrenia, and reduce the stigmatization experienced by both patients and therapists in the field. In addition, experts by experiences will increase the hope for current patients treated in EIS and affect the treatment culture in a positive direction. An early intervention youth mental health service in Melbourne uses families as partners in mental health care in close collaboration with clinical teams to provide new family members with a range of interventions to assist recovery, their experience that new families asked for contact with peer-families very early in the course of treatment [111].

#### A phase-specific individual tailored treatments course in OPUS YOUNG

OPUS YOUNG treatment is a complex intervention that allows to be tailored to the individual patient. Therefore, many different courses of treatment can take form. Table 3 shows an example of how the two years intervention could proceed.

#### Table 3 Example of OPUS YOUNG treatment for two years

#### **Example of 2-years OPUS YOUNG treatment**

Mandatory for all patients A motivated option When motivated and able, flexible start time According to individual needs

#### Treatment as usual (TAU)

Participants allocated to the standard treatment will be offered the existing treatment in CAMHS. According to the Specialty Plan for child and adolescent psychiatry by the Danish Health Authorities, 2019 [112] children and adolescents with psychosis will be referred to a predefined level of care in the Danish health care system according to the severity and complexity of their psychotic illness. In essence, the individual patient will be referred to the unit in CAMHC that best fits the level of care indicated. In Denmark, three levels of care may be provided: *Main function, regional function, or highly specialized function*. If the needs of a patient change during the course of illness, the patient will be transferred to a higher or lower level of care. The treatment follows national Danish guidelines and local guidelines but is not manualized. None of the levels of care in TAU are currently assertive as a standard. The unit for highly specialized function for children and adolescents with schizophrenia in CAMHC manages the patients with the most severe psychotic illness. In addition to standard treatment, this unit is specialized by providing a multidisciplinary team, case-management (no defined upper case-load), family support and psychoeducation, in addition to psychopharmacological treatment. In some cases, social skills training and CBT may be offered. In general, office visits take place in outpatient clinics. The main and regional functions are both at a less intensive level of care than the highly specialized function, and standard treatment usually offers psychoeducation, antipsychotic treatment, and some support to the families. The outpatient units proving the TAU plans to implement an adjusted and transdiagnostic version of flexible assertive community treatment (F-ACT) building on reports from Danish adult mental health services [113] and models from Dutch youth mental health services [114]. The establishment of F-ACT teams in TAU are expected to be initiated in September 2021.

#### **Fidelity monitoring**

We will assess the fidelity of the OPUS YOUNG treatment and structure during the trial period, using an special OPUS YOUNG modified version (Appendix 2) of The Danish Fidelity Scale for Specialized Early Intervention Team [115–117]. To lower the possibility of idiosyncratic judgement, two assessors will independently conduct the fidelity assessment once a year, and their interrater reliability will be measured. Further we will assess fidelity of core parts of the treatment; CBCM, SCIT and Family intervention to guide and maintain adherence to the OY intervention throughout the trial period. Furthermore, meetings and co-rating will be arranged to ensure program fidelity and interrater reliability.

#### Recruitment of staff, training, and preparation of OPUS YOUNG treatment

Since January 2019 an OPUS YOUNG manual including all treatment elements suiting the target group has been developed. The first OPUS YOUNG team has been established, and they have tested the OPUS YOUNG intervention since January 2020. The team has participated in the final preparations of materials and are qualified and educated in the manual-based OPUS YOUNG treatment, and ready for including patients by June 2021. The first team will be on-going throughout the entire trial period and will get an important status as a critical mass that can help with the introduction of the new team members and guide their education in the manual-based treatment. Recruitment of additional multidisciplinary staff will take place gradually relative to the number of patients included in the experimental treatment (see figure 2).

The OPUS YOUNG staff will in addition to their clinical profession be educated and trained in cognitive behavioural therapy as well as the core elements of the OPUS YOUNG treatment: CBCM, MFG, SCIT, MOVE, and the psychoeducational family-based involvement. Moreover, training of staff will include: the overall program principles of early intervention services, psychopathology and how to work together as a team of health professionals with different and

overlapping roles. Ongoing training and supervision will ensure that the staff is qualified to perform the core elements of the treatment. The OPUS YOUNG team will develop material and videos for use in the SCIT-treatment.

#### Cooperation with the OPUS organization for adults

The OPUS YOUNG team will have close collaboration with the Danish OPUS teams for adults aged 18-35 years and benefit from their 20 years of experience and competence in EIS. Experts from the OPUS team together with experts in cognitive behavioural therapy, will initially and on-going, train, teach and supervise the OPUS YOUNG staff in the function as CBCM. Likewise, experienced multifamily group-therapists from the OPUS team will teach and supervise OPUS YOUNG staff in how to lead and facilitate a multifamily-group. OPUS YOUNG team leaders will attend the OPUS-leader meetings, which again will facilitate cooperation, increase the possibility for knowledge to be shared and developed between teams and bridge the age spread. The OPUS YOUNG staff will participate in the annual national OPUS conferences. A close collaborating will strengthen the overall specialized early intervention efforts for young people with the first episode of psychosis in Denmark.

**Figure 2 Expected number of patients in OPUS YOUNG intervention during the 26 months of recruitment.** OPUS treatment team 1 will be engaged from June 2021 to September 2025. OPUS treatment team 2 will be engaged in the expected two-year period when the patient volume is above 71 patients.

#### Hierarchy of outcome measures

#### **Primary outcome**

The primary outcome is change in the estimate of the adolescent's social function, measured with Personal and Social Performance Scale (PSP) [43]. PSP provides a global score on a scale from 1-100, with lower scores indicating lower social functioning, as well as scores on four subdomains (Socially useful activities, Personal and social relationships, Self-care, and Disturbing and aggressive behaviour) on a scale 6-point Likert scale. The scoring of PSP is based on all available information and concerns the patient's daily level of functioning in the family, in school, and during leisure time during the past month. Researchers will interview the participants prior to the scoring of PSP using a semi structured interview guide suitable for children and adolescents, developed by the OPUS YOUNG research team. The final PSP-score will be determined using consensus rating, by which the rater will discuss the PSP score with an experienced user of PSP (the co-PI of the OPUS YOUNG study) and/or a senior consultant and other researchers from the research team. Prior to the initiating the OPUS YOUNG study, we will conduct a pilot-study to ensure that the assessors have a high level of inter-rater reliability with ICC values for the primary outcome measure of at least 0.70, prior to working as assessors in the trial (ICC is calculated in SPSS using two-way mixed models for absolute agreement on single measures). Assessors at entry and at the follow-up interviews will be independent and blind to treatment allocation. Patients will be instructed to maximize efforts to keep their treatment allocation unknown for the investigator.

*Secondary outcome measures*: Positive symptoms, negative symptoms, and disorganized symptoms (SAPS and SANS); client satisfaction (CSQ); and quality of life (KIDSCREEN-10).

#### Exploratory outcomes:

Affective symptoms (YMRS, HAM-6); global psychopathology (CGI-S, CGI-I); duration of untreated psychosis (IRAOS); global cognitive functioning (BACS total score); social cognition (Hinting Task and EIMT); general self-efficacy (GSE); patient and clinician rated treatment alliance (WAI); negative effects of psychological treatment (NEQ); school adherence; parental stress (PSS); family function (FAD); quality-adjusted life year (CHU9D and EQ5D); executive functioning (BRIEF); socially useful activities, personal and social relationships, self-care, disturbing and aggressive behaviours (PSP subscales); use of psychopharmacological treatment; substance abuse; and the use of psychiatric and social services.

#### Sample size calculation

Based on the literature concerning the level of psychosocial dysfunction measured with PSP in early onset psychosis (EOP) [118–121] we expect a Standard Deviation (SD) on PSP around SD=13. Concerning the expectations on relevant group difference in improvement during two years of EIS [6,122] we have evaluated the minimal relevant difference (MIREDIF). MIREDIF should represent a meaningful minimal group difference in response in the sense that it would justify a choice between two interventions in a clinical setting. The total PSP scale score range from 1 to 100. The metanalysis [6] on EIS interventions found, for functional outcome measured with Global Assessment of Functioning (GAF, scaled 1-100) including n=1005 participants in 7 studies, a standardized mean difference (difference in mean outcome between groups/standard deviation in outcome among participants) of 0.21 (in the individual 7 studies included ranging from 0.02 to 0.56). With a SD of 13, this equals an expected difference in PSP scores between groups of around 2.73, ranging from 0.26 to 7.28. Based on these findings and the evaluation of what is clinically meaningful when regarding the PSP 10-point ranges of functioning we have decided that it would be clinically relevant to be able to detect a difference of 5 points in outcome score on the total PSP scale between the two interventions. Using a power of 90% and a two-sided alpha of 5%, and expecting a SD of 13 on PSP, the required sample size necessary to detect or reject a difference of at least 5 points between the OPUS YOUNG and TAU group on PSP at endpoint is 284, why we

plan to enrol a minimum of 142 patients in each group. However, to account for drop-outs and due to our relatively long recruitment procedure time, where patients are referred from the clinic and may wait during the assessment period being offered participation, we will include up to 152 patients in each group if necessary, within the recruitment period. This will ensure that patients who are in the recruitment process will still be offered participation in the study even if the minimum of 284 participants has already been enrolled. This is ethically more proper, as patients in the centre entering the recruitment procedure are informed about the potential possibility to be offered inclusion in the study. The last patients will be assessed and included by September 1st, 2023. After this, no more patients will be included.

The required sample size was estimated as follows (N=total sample size, SD=standard deviation of the outcome measure,  $\alpha$ =type 1 error,  $\beta$ =type 2 error, MIREDIF=minimal relevant difference of outcome measure, z = fractiles in normal distribution), when assuming equal sample sizes, equal SDs for the two interventions, and  $\alpha$ =0.05 and  $\beta$ =0.10:

$$N = 4 \times (z_{1-\alpha/2} + z_{1-\beta})^2 \times (\frac{SD_1}{MIREDIF})^2$$

The required sample size with an estimated SD of 13 and a MIREDIF of 5:

$$N = 42 \times (\frac{13}{5})^2 = 284$$

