#### Handling of study drop-out:

Based on data from a prior study (the TEA trial) of 113 patients with first-episode psychosis aged 12-17 years conducted in our CAMHS in the period 2010-2014 we have evaluated the expected study drop-out in the OPUS YOUNG trial. The TEA trial compared the beneficial and harmful effects of two antipsychotics, aripiprazole versus quetiapine, in a 12-week study. The drop-out rate (lost to follow-up assessments at week-2, week-4 or week-12) was 14% and 10%, respectively. In the TEA trial missing data was handled by intention-to-treat-analysis and multiple imputations [123]. In the OPUS YOUNG study, including an identical group of participants, we expect a drop-out rate of approximately 10%. We expect that the combination of pharmacological and psychosocial treatment in both intervention arms will motivate the patient and family to adhere to treatment. Furthermore, even though the drop-out rate for the two-year adult OPUS study was approximately 30%, our experience from the clinic is that parents intensively support young patients to adhere to treatment and support continued participation in clinical trials.

As we scientifically and ethically find it important to strive to include the most exact needed number of participants possible, not too few (risk of loss of statistical power), not to many (risk of burdening too many patients with engagement in a RCT) we will handle missing data as a result of study drop-out by performing intention-to-treat analysis with multiple imputation of missing data [124]. See also section on statistical analysis below.

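### The 90% power for PSP is attached to 284 enrolled, but 284 is the number needed with a 24-month score; at the expected 10% drop-out the protocol's own inputs give 87% (284 enrolled) to 89% (304 enrolled)

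*Protocol*

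**What the plan says.** The protocol, under Sample size calculation, sets the target as follows: "Using a power of 90% and a two-sided alpha of 5%, and expecting a SD of 13 on PSP, the required sample size" to detect a 5-point difference between the "OPUS YOUNG and TAU group on PSP at endpoint is 284". The formula printed there assumes equal arms and equal SDs. It has no term for drop-out, baseline adjustment or repeated measurement.

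The same number then becomes the enrolment floor: the investigators "plan to enrol a minimum of 142 patients in each group". Partly because of drop-outs and partly because of the long recruitment process, "we will include up to 152 patients in each group if necessary, within the recruitment period". Table 4 (Power calculation) lists PSP with a difference of 5.0, SD 13, N of 2*142 and power 90%.

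Under Handling of study drop-out, the protocol says "we expect a drop-out rate of approximately 10" per cent. It wants the number of participants to be "not too few (risk of loss of statistical power") and not too many, and concludes that "we will handle missing data as a result of study drop-out by performing intention-to-treat analysis with multiple imputation of missing data".

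**The concern.** A sample size formula without a drop-out term returns the number of patients who must contribute an endpoint value. The protocol derives 284 in that sense and then uses it as the number to enrol, while expecting about one in ten patients to be lost. The 90% in the text and in Table 4 therefore holds only if all 284 enrolled patients have a 24-month PSP, which the protocol itself does not expect.

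The rise to 304 is conditional, and drop-out is only one of its two stated reasons. The protocol recognises the risk to power but answers it with multiple imputation. Under a missing-at-random assumption, imputation deals with bias and uses whatever auxiliary data exist. It does not by itself restore endpoint information that was never collected.

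Readers will rely on the stated 90% (PSP) and 80% (SANS) when they interpret a null result, so these figures should match the number of patients expected to have endpoint data.

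**Working it through.** **Inputs.** From Sample size calculation: difference 5 points, SD 13, two-sided 5%, power 90%, enrolment 142 to 152 per arm. From Handling of study drop-out: loss of about 10%. From the SAPS, SANS section and Table 4: SANS difference 0.4, SD 1.2.

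**Step 1: reproduce the protocol's figure.** N = 4 × (1.960 + 1.2816)² × (13/5)² = 284.1. With the rounded constant in the protocol, 42 × 2.6² = 283.9. The 284 is correct.

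**Step 2: how much loss 304 covers.** 1 − 284/304 = 6.6%, which is less than the expected 10%. Keeping 284 with endpoint data at 10% loss needs 284/0.90 = 315.6, so 316 enrolled.

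**Step 3: PSP power after loss.** Power = Φ(d / (SD × √(2/n)) − 1.960), where n is the number per arm with a 24-month PSP. The difference detectable at 90% power is 3.2415 × 13 × √(2/n).

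| Enrolled | Loss | n per arm with endpoint | Power | Detectable at 90% |
|---|---|---|---|---|
| 284 | none | 142 | 90.0% | 5.00 |
| 284 | 10% | 127.8 | 86.7% | 5.27 |
| 304 | 10% | 136.8 | 88.9% | 5.10 |

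For example, at n = 127.8: 5 / (13 × √(2/127.8)) = 3.0745; 3.0745 − 1.960 = 1.1145; Φ(1.1145) = 0.867.

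**Step 4: sensitivity to the SD.** The protocol says "we expect a Standard Deviation (SD) on PSP around SD=13". At 10% loss, an SD of 12.5 gives 89.2% (284) and 91.1% (304). An SD of 13.5 gives 84.2% and 86.5% (86.50% before rounding). The restated figures are therefore approximate.

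**Step 5: possible offset from the planned model.** Statistical analyses specifies a mixed model that includes baseline values. If baseline and 24-month PSP correlate at r, the SD becomes 13 × √(1 − r²). At 10% loss, 90% power is regained when r is about 0.32 (284) or 0.19 (304). The protocol gives no r, so these are break-even values, not estimates.

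**Step 6: possible recovery from the 12-month PSP.** If all patients without a 24-month score have a 12-month score, and the two correlate at 0.3 to 0.7 (an assumption), the variance is multiplied by 1 + (0.1/0.9)(1 − r²) relative to no loss. Power is then 87.0% to 88.4% (284) or 89.2% to 90.4% (304).

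**Step 7: SANS.** With d = 0.4 and SD 1.2, power is 80.2% with no loss at 284. At 10% loss it is 76% (284) or 79% (304).

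**The case against.** The strongest reply is that nothing here is miscalculated. The formula, the 284 and the PSP row of Table 4 all agree with the stated inputs. The protocol discusses drop-out openly, allows up to 304 partly for that reason, and explains that it does not want to burden more young patients than necessary. At 304 the shortfall is only 1.1 percentage points, and at either number it is comparable with the effect of moving the SD by half a point.

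The 87% and 89% are also not the power of the planned analysis. They describe an unadjusted comparison of patients with a 24-month score, whereas the protocol plans a repeated-measures model with baseline included and a 12-month PSP. A modest correlation would bring power back to 90%.

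Much of this stands. The shortfall is small, the reason for not enrolling more is legitimate, and the restated figures must be labelled as unadjusted. What does not stand is the 90% as printed. It comes from the unadjusted formula applied to patients with endpoint data, yet it is attached to patients enrolled. The 304 is optional, covers less than the expected loss, and is not the number used in Table 4. The adjusted model may recover the difference, but without a stated correlation the protocol does not show that it does. The conflict lies between sections of the protocol itself, so it does not depend on what an SAP may contain.

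**Conclusion.** The point holds, and its size is modest. The 284 is right as the number needed with a 24-month PSP. It is wrong to pair 284 enrolled with 90% power while expecting about 10% drop-out. On the stated inputs and the unadjusted formula, power is about 87% with 284 enrolled and 89% with 304, a loss of about 3 points and 1 point.

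This assumes 10% loss in each arm, SD 13, and no gain from baseline or 12-month data. With such gains the planned analysis could reach 90%; with a larger SD or more drop-out it would fall further short. As one sensitivity case only, the rate of about 30% seen in the adult two-year study, which the protocol sets aside with reasons, would give 77% (284) or 80% (304).

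SANS was planned with no margin and falls below 80% at either enrolment number. CSQ stays above 99%, and KIDSCREEN-10 moves only from 99% to 98%. SAPS cannot be restated yet because its SD is 1.4 in the text and 1.2 in Table 4. At 1.4, power with 284 is 67% even without any loss.

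**What to change.** Leave enrolment and analysis unchanged and correct the statements.

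1. In Sample size calculation and Table 4, say that 90% assumes 284 patients with a 24-month PSP and no baseline adjustment. Beside it give the power at the expected 10% loss: about 87% for 284 enrolled and 89% for 304, labelled as unadjusted figures from the protocol's formula.
2. Alternatively, base the 90% on the planned baseline-adjusted mixed model, with a correlation justified from data. At 10% loss it must be at least about 0.32 (284) or 0.19 (304). These break-even values do not themselves justify a choice.
3. In Handling of study drop-out, describe multiple imputation as the method for handling missing data, not as the protection against loss of power.
4. In Table 4, restate SANS on the same basis: 76% at 284 and 79% at 304. For SAPS, first reconcile the two SDs against their source, then restate its power.

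The cost is some protocol wording and one table, plus a check of the SAPS source. The stated PSP power falls by 1 to 3 points unless it is based on the adjusted model.
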